#### 13.2 Withdrawal Procedures:

If a subject withdraws their consent, study staff will no longer use or disclose their health information. However, information already collected cannot be retrieved or destroyed and may be used as part of the study.

#### 13.3 Termination Procedures:

The study may terminate early and at any time for administrative reasons. In the event that this occurs, the IRB will be notified of this decision.

#### 14.0 Risks to Participants

14.1 Foreseeable Risks: Foreseeable risks to participants include loss of confidentiality of their responses, as collected during the RCT. The likelihood of the loss of confidentiality will be low because of the research processes detailed below.

Participants will be sent a link via encrypted email to the websites being studied (the intervention occurs via Zoom). The websites are available to the public. When the intervention is done remotely the participant will share their screen with the research coordinator using a password protected video conference service such as Zoom. Participants will be instructed to shut down all other programs and pages so as not to accidently share other information on their computer with the research coordinator. The coordinator will take notes on which pages of the website are viewed and how long participants took to respond to the questions posed. The responses to survey questions and knowledge questions will be recorded by the coordinator on paper that only has the unique study code and no personal identifiers. Thus, no names will be attached to the surveys,—they will be labeled only with the unique study code. The identifiers for the respective subjects will be kept separately. The Zoom conference call will be recorded (audio and video), and stored on a HHRI computer or server.

The randomized clinical trial participants will be instructed not to use their full names since the intervention will be recorded. The recordings will be used to determine whether the study procedure was followed correctly. For example, the recordings will be reviewed to ensure that there were no prompts given inadvertently to the participant to help the participant get the correct answer. The recordings will also be reviewed to determine locations in the websites that were difficult for the participant to navigate.

14.2 Reproduction Risks: N/A

14.3 Risks to Others: N/A

#### 15.0 Incomplete Disclosure or Deception

15.1 Incomplete Disclosure or Deception: N/A

## 16.0 Potential Benefits to Participants

#### 16.1 Potential Benefits:

Despite the availability of best medical care, patients with end-stage disease have difficulty finding transplant centers that transplant patients like them. The cost of caring for these end-stage disease patients is high and transplantation is cost-effective and life-saving. Participation in the study confers no direct benefit to the study subjects.

Understanding the needs of transplant candidates and creating a patient friendly website that allows them to find transplant centers that transplant patients like them, will be useful for all future transplant candidates. This study could improve access to transplantation and potentially improve outcomes post transplantation. Given the lack of direct benefit to study participants, it is important to recognize that the risks are also minimal, the major risk being loss of confidentiality. The safeguards planned will minimize this risk.

#### 17.0 Statistical Considerations

#### 17.1 Data Analysis Plan:

Before initiating outcome analyses, we will perform exploratory analysis to examine frequency distributions for all baseline variables, with particular attention to variable ranges and skewness. We will examine group comparability at baseline between the two RCT arms to assess whether randomization succeeded in creating equivalent groups. These analyses will help determine potential need to incorporate additional covariates in later analyses using propensity-based methods (22-25). Relevant baseline measures include socio-demographic factors, health literacy and numeracy assessment, and baseline survey information.

17.2 Power Analysis: The table shows the required sample size for ranges of detectable differences and within-person correlation.

						Correlation		
							0.	
		0.0	0.1	0.2	0.3	0.4	5	0.6
	0.20	107	98	89	79	67	56	45
Detectable	0.22	90	82	76	66	56	47	38
Difference	0.24	76	71	64	55	48	40	33
	0.25	70	66	59	51	44	37	*
	0.26	66	61	55	48	41	34	*
	0.28	57	53	46	41	35	30	*
	0.30	51	45	41	36	32	27	*

On the conservative side, we will power the study to detect a proportional difference as small as 25% and therefore plan to enroll at 72 subjects. Recruitment will continue until this desired sample size is achieved.

## 17.3 Statistical Analysis:

The primary analysis will be based on the conservative "intention-to-treat" (ITT) approach. We will use a chi-square test and logistic regressions for analyzing primary and secondary measures. A sensitivity analysis will be conducted excluding subjects that did not enter the correct hypothetical information into the website. The research coordinator will record the amount of time subjects spend with each website and the webpages viewed by each subjects and that information will be analyzed for descriptive analysis. Other subset analysis will be conducted but presented as ad hoc analysis.

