## 3.0 Study Endpoints/Events/Outcomes

- 3.1 Primary Endpoint/Event/Outcome: The primary outcomes are two separate assessments of the comprehension of the report card. To assess comprehension, the correct response to the following type of question will be assessed, "Which of the following transplant centers have the most experience with transplanting candidates over age 70?" There will be one correct answer; respondents will be told to assume they are in a specific zip code or state and are over age 70 and then asked to choose one of the several transplant center report cards shown or respond "Don't know." Another example of the question used to assess comprehension will be used, "Which of the following transplant centers have the most experience with transplanting candidates with body mass index (BMI) over 40?" There will be one correct answer; respondents will be told to assume they are in a specific zip code or state and have a BMI over 40 and then asked to choose one of the several transplant center report cards shown or respond "Don't know." Similar measures used previously by [name], to determine the best way to present report cards to the general public (17). We will also determine comprehension of key concepts in the reports, to identify participants' ability to determine whether a center performs transplants on "patients like me."
- 3.2 Secondary Endpoint(s)/Event(s)/Outcome(s): Perceived value of information will be determined via patient responses to the following question, "How useful is the information in the report card in helping you choose a transplant center for you or your family?" Response choices to the questions will be based on a 5-point Likert-type scale (Example: 1 = not at all useful to 5 = very useful). We will also measure satisfaction with decision-making and decisional conflict using the effective decision subscale of the Ottawa Decisional Conflict Scale, which has been validated in multiple studies (18-21).

These questions will be written on cards if the intervention is conducted face-to-face. If conducted via HIPPA compliant zoom call, the questions will be placed in the chat box for the subject to refer to them during the intervention.

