## 4.0 Study Intervention(s)/Interaction(s)

#### 4.1 Description:

Before the intervention, the study design with use of hypothetical scenarios will be explained to the participant. The concept of randomization will be also be explained. The participants will be asked a few questions to assess their understanding of the study design, specifically the hypothetical nature of the scenarios. We will also assess whether they understand the concept of being randomized to see one

website first and then the other. Only those participants that understand the study design will be invited to participate in the intervention and will be randomized. For subjects that are randomized, a survey will be administered verbally to collect demographic information and information about their kidney disease and comorbidities. The functional health literacy and numeracy assessment and health status questionnaire will be completed. Subjects will be stratified by the transplant center site and then block randomized. One group will be shown the existing SRTR website with its existing SRTR report cards and then the website with the new patient-centered AHRQ report cards for kidney transplants. The other group will be shown the two websites in opposite order. Each participant will have at most 30 minutes to view each of the websites. After viewing each website, responses to the intervention will be collected. Sessions where participants are reviewing the websites will be recorded using Zoom. Figure 2 shows the study design whereby subjects will be block randomized once to one of the four groups consisting of 18 subjects each. At the end of the study, the patients will have access to both the websites.

The study interventions can be administered in person on a laptop. During the COVID-19 pandemic, the intervention can be administered remotely via email and zoom. The link to the websites will be sent via encrypted email and the intervention will be recorded via zoom. The recordings for subjects at Hennepin Healthcare will be stored on computers at that site.

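### Section 17.3 names a chi-square test and logistic regressions with no pairing or clustering by subject, although each subject answers after both websites and the trial was sized on paired responses

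*Combined protocol and SAP*

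**What the plan says.** Section 17.3 gives the outcome analysis in one sentence: "We will use a chi-square test and logistic regressions for analyzing primary and secondary measures". The rest of that section covers intention-to-treat, a sensitivity analysis, descriptive data on viewing, and ad hoc subsets. It names no paired test, subject effect, clustered variance, or term for viewing order.

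The design is within-subject. Section 4.1 has every participant see both websites, with only the order randomized, and says: "After viewing each website, responses to the intervention will be collected". Section 17.2, which repeats the table of Section 11.1, is sized on that basis: "The table shows the required sample size for ranges of detectable differences and within-person correlation". It concludes: "we will power the study to detect a proportional difference as small as 25% and therefore plan to enroll at 72 subjects".

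The unit of analysis is less clear. Section 3.1 says "The primary outcomes are two separate assessments of the comprehension of the report card", one about age over 70 and one about BMI over 40. Section 4.1 says "subjects will be block randomized once to one of the four groups consisting of 18 subjects each". Neither section says whether the two questions are combined in one test or tested separately. The text of Figure 2 does not survive well enough to show whether a subject gets the same question after both websites.

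For secondary measures, Section 3.2 says of the usefulness item: "Response choices to the questions will be based on a 5-point Likert-type scale". Section 17.3 applies the same two methods to these.

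**The concern.** A sample size that falls as within-person correlation rises belongs to a paired comparison. An ordinary chi-square test or logistic regression on the pooled responses ignores that correlation. Its standard error for the website contrast is then too large if the correlation is positive and too small if it is negative. As written, the analysis in 17.3 is not the one that 17.2 sizes.

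Two things are at stake. One is precision: intervals that are too wide, and lost power for effects below 25 points. The other is what the 72 stands for. If the two questions are tested separately and each subject keeps one question, there are 36 pairs per question. The smallest number printed in the plan's own 25-point row is 37, at correlation 0.5; the others run up to 70.

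**Working it through.** **Inputs.** From the documents: 72 subjects in four groups of 18, two responses per subject, a binary outcome (correct or not), a planned difference d = 0.25, and the table in 11.1 and 17.2. Assumed, because the documents give none of them: two-sided 5%, 80% power for the table check, and proportions correct of 0.5 − d/2 and 0.5 + d/2.

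**1. Reproducing the sample-size table.** With p1 = 0.5 − d/2, p2 = 0.5 + d/2 and within-person correlation r, the discordant probabilities are

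- p10 = p1(1 − p2) − r·√(p1(1 − p1)p2(1 − p2))
- p01 = p2(1 − p1) − r·√(p1(1 − p1)p2(1 − p2))

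The exact two-sided McNemar test refers the split of the m discordant pairs to Binomial(m, ½). Its power is averaged over m ~ Binomial(n, p10 + p01). The smallest n for 80% power compares with the plan as follows:

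| d | Correlations | Plan | Calculated |
|---|---|---|---|
| 0.20 | 0 to 0.6 | 107, 98, 89, 79, 67, 56, 45 | 107, 97, 88, 79, 68, 57, 45 |
| 0.25 | 0 to 0.5 | 70, 66, 59, 51, 44, 37 | 71, 65, 58, 51, 44, 37 |
| 0.30 | 0 to 0.5 | 51, 45, 41, 36, 32, 27 | 51, 46, 41, 36, 32, 27 |

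All 45 printed numbers agree within 1 subject, and power at the printed n runs from 0.793 to 0.818. The asterisks also fit. At d = 0.25 and r = 0.6, p10 = 0.375 × 0.375 − 0.6 × 0.234375 = 0, and it is negative for larger d. An unpaired calculation has no correlation term and cannot produce these columns.

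**2. Interval width at 25 points, 72 pairs.** Each proportion has variance 0.375 × 0.625 = 0.234375.

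- Pooled half-width: 1.96·√(2 × 0.234375/72) = 15.8 points at any r.
- Paired half-width: 1.96·√(2 × 0.234375 × (1 − r)/72) = 15.8, 13.2 and 11.2 points at r = 0, 0.3 and 0.5.
- Ratio 1/√(1 − r): pooled is 0%, 20% and 41% too wide.

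**3. Type I error and power, questions combined (72 pairs).** The pooled and McNemar figures are exact enumerations. The GEE figures are simulated with 10,000 replicates per cell. That model has website, period, question and site terms, independence working correlation, robust variance times n/(n − k), and t with n − k degrees of freedom. The simulation assumes the same question at both viewings and a 50/22 site split. Each cell gives r = 0, 0.3, 0.5.

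| | Pooled chi-square | Exact McNemar | GEE |
|---|---|---|---|
| Type I error | 5.5%, 2.2%, 0.7% | 3.3%, 3.0%, 2.9% | 4.4%, 4.2%, 4.3% |
| Power, 20 points | 69%, 72%, 76% | 61%, 76%, 90% | 65%, 80%, 92% |
| Power, 25 points | 87%, 91%, 95% | 81%, 93%, 99% | 84%, 95%, 99% |

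**4. Questions separate, each subject keeping one question (36 pairs each), 25 points.** Power at r = 0, 0.3, 0.5:

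- Pooled chi-square: 56%, 56%, 57%.
- Exact McNemar: 47%, 62%, 79%.
- GEE with website and period: 50%, 69%, 86%.

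Exact McNemar with 36 pairs first reaches 80% power at differences of about 35.5, 30 and 25.5 points.

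**5. Questions separate, each subject switching question between viewings.** Each per-question comparison is then 36 against 36 different subjects. An ordinary chi-square is valid for it, with about 56% power at 25 points.

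**The case against.** The strongest reply is that 17.3 is brief rather than wrong. A chi-square test can mean the McNemar form, logistic regression can be conditional or clustered, and authors who sized on within-person correlation plainly knew the responses were paired. That is fair as to intent, but nothing in the text commits the analyst to it.

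Second, pooling does little damage at the planned effect. It is conservative for positive correlation, its type I error does not exceed 5.5% in these calculations, and at correlation 0 it has more power than either alternative. This stands, and it limits the severity.

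Third, the power shortfall at 25 points arises only if the questions are analysed separately, which is a matter of endpoint definition as much as pairing. The 36-pair case also requires each subject to keep one question. Both conditions stand. But under switching a per-question test has only about 56% power, so neither separate-question reading generally delivers what 17.2 implies.

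Fourth, exact McNemar is a strict comparator. At 36 pairs and correlation 0.5, the asymptotic form has 86.7% power and the mid-p form 86.3%, so falling below 80% there is specific to the exact test. At correlation 0 and 0.3 the clustered GEE is also below 80%.

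Last, the table match rests on inferred inputs that are not unique. With the lower proportion fixed at 0.34, four entries differ by 2, and a normal-approximation McNemar formula at 85% power with lower proportion 0.29 fits as well. Both candidates are paired, so the conclusion about the basis of the table is unaffected.

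**Conclusion.** The concern holds and should be fixed; it does not invalidate the trial. The analysis named in 17.3 is not tied to the paired comparison that 17.2 sizes. For the combined analysis the cost of pooling is intervals 20% to 41% too wide at correlations 0.3 to 0.5, and lower power below the planned effect (76% against 90% for exact McNemar at 20 points and correlation 0.5). Power at 25 points is not at risk.

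The larger exposure is the undefined unit of analysis. The 72 gives the power in the table only if the two questions are combined. With 36 pairs per question, exact McNemar stays below 80% at 25 points for correlations 0 to 0.5, although at 0.5 the shortfall is marginal and depends on the test. A reader of 17.2 and 17.3 cannot tell which analysis the power statement covers. The figures assume proportions centred on 50% and a two-sided 5% level.

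**What to change.** In 17.3:

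- Name one primary website contrast: a logistic GEE clustered by subject, with independence working correlation, small-sample-corrected robust standard errors, and terms for website, viewing period and question. It can be used whether the question is repeated or switched.
- Add a site term only if more than one site contributes. Section 4.1 ("Subjects will be stratified by the transplant center site and then block randomized") and Section 18.4 (50 of the 72 from HHS) imply more than one; Sections 23.1 and 24.1 name only HHS.
- State whether the same question is asked after both websites. If so, give McNemar as an unadjusted check; if not, omit it.
- State that the two questions are combined (72 pairs) for the primary contrast, that 17.2 refers to that analysis, and that per-question results are estimates with intervals. If they are to be tested separately, give the power for 36 pairs, or for 36 against 36 if the question switches.
- For secondary measures collected after each website, use an identity-link GEE clustered by subject (mean difference) for the usefulness item and the decisional-conflict subscale score.
- A first-viewing comparison (36 against 36, about 56% power at 25 points) is optional and supportive only.

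The cost is SAP wording and a few lines of code, since website, order, question and site are known for every subject. The combined analysis needs no change in sample size or procedures. If the correlation is near zero, there is a small loss of power at 25 points: 84% for GEE and 81% for exact McNemar, against 87% pooled.

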#### 17.4 Data Integrity:

The PI is responsible for the integrity of the data for this study. The study recordings will be used to determine whether the study procedure was followed correctly. For example, the recordings will be reviewed to ensure that there were no prompts given inadvertently to the participant to help the participant get the correct answer

The recordings will be stored. If the recordings are presented in publications and presentations, the presented recordings will focus on the website that subjects are navigating but without the subject's voice and face being shown. These recordings can highlight strengths and weaknesses of the websites in order to motivate future improvements to the web site.

18.0 Health Information and Privacy Compliance Individually Identifiable Health Information:

Under the HIPAA Privacy Rule, research studies are permitted to use and disclose protected health information with the authorization of the research participants, or without individual authorization in limited circumstances. Outside of that none of this information will be released outside of the covered entity.

18.1	Select which of the following is applicable to your research:
	☐ My research does not require access to individual health information and therefore assert HIPAA does not apply.
	oxtimes I am requesting that all research participants' sign a HIPCO approved HIPAA
	Disclosure Authorization to participate in the research (either the standalone form or the combined consent and HIPAA Authorization), only if IRB does not grant waiver of consent.
	$\square$ I am requesting the IRB to approve a Waiver or an alteration of research participant authorization to participate in the research.
	$\Box$ An external IRB (e.g. Advarra) is reviewing and we are requesting use of the authorization language embedded in the template consent form in lieu of the U of M stand-alone HIPAA Authorization. Note: External IRB must be serving as the privacy board for this option.
18.2	Identify the source of Private Health Information you will be using for your research (Check all that apply)
	☐ I will use the Informatics Consulting Services (ICS) available through CTSI (also referred to as the University's Information Exchange (IE) or data shelter) to pull records for me
	oxtimes I will collect information directly from research participants.
	☐ I will use University services to access and retrieve records from the Bone Marrow Transplant (BMPT) database, also known as the HSCT (Hematopoietic Stem Cell Transplant) database.
	oxtimes I will pull records directly from EPIC.
	$\square$ I will retrieve record directly from axiUm / MiPACS
	$\square$ I will receive data from the Center for Medicare/Medicaid Services
	$\square$ I will receive a limited data set from another institution
18.3	Explain how you will ensure that only records of patients who have agreed to have their information used for research will be reviewed.

Please see pertinent recruitment and screening sections above. Within EPIC, research team members will first look at a potential participant's "Patient Type" to determine if he or she has opted in or opted out of research. If the potential participant has not opted out of research, preliminary screening will take place prior to the research team approaching the potential participant. If a potential participant has opted out of research, the research team will not look into the chart and will not be able to do preliminary screening. Instead, the researcher will approach the potential participant in person to ascertain interest in the study. If the potential participant expresses interest in the study, the researcher will inform the potential participant that his or her medical record will be reviewed to determine eligibility and ask for the potential participant's permission to view his or her medical record for this purpose.

18.4 Approximate number of records required for review:

There are approximately 300 kidney transplant candidates on the waiting list at at HHS. The records of these candidates will be screened to enroll 50 of the 72 subjects in the RCT

i	n the RCT.
18.5	Please describe how you will communicate with research participants during the course of this research. Check all applicable boxes
	$\hfill\Box$ This research involves record review only. There will be no communication with research participants.
	Communication with research participants will take place in the course of treatment, through MyChart, or other similar forms of communication used with patients receiving treatment.
	☑ Communication with patients will take place in-person, via phone, video conference calls, through mail, and encrypted email. Email communication will be used to share initial details about the study (if the patient is approached by a care team member and would like to hear from the study team via email), the Zoom session information, and to provide patient compensation following their study session if they prefer to be compensated by email.
18.6	Access to participants:
	Investigators have permissible access to patient records via EPIC and their treating relationship with the patients. Research team members have EPIC access via NERS and will only access records and PHI as outlined in the protocol above.
18.7	Location(s) of storage, sharing and analysis of research data, including any links to research data (check all that apply).
	☐ In the data shelter of the Information Exchange (IE)
	☐ Store ☐ Analyze ☐ Share

PROTOCOL TITLE: HSR # 16-4130 Testing a Patient-Centered Report Card for Solid Organ Transplant C-candidates Among Kidney Transplant Candidates **VERSION DATE:** ☐ In the Bone Marrow Transplant (BMT) database, also known as the HSCT (Hematopoietic Stem Cell Transplant) Database ☐ Analyze ☐ Store □ Share ☑ In REDCap (recap.ahc.umn.edu) ☐ In Qualtrics (qualtrics.umn.edu) ☐ Analyze □ Share ☐ Store ☐ In OnCore (oncore.umn.edu) ☐ Store ☐ Analyze ☐ Share ☐ In the University's Box Secure Storage (box.umn.edu) for M-Health patients ⋈ Share ☐ Store Share ☐ In an AHC-IS supported desktop or laptop. Provide UMN device numbers of all devices: ☐ Store ☐ Analyze ☐ Share Other: Data will be maintained in paper, digital, and audio formats. De-identified data collected on paper will be transferred to a database stored on a secure server at Hennepin Healthcare Research Institute (HHRI). Paper data will be stored in filing cabinets in the researchers' locked offices. All computers require users to log-in with usernames and passwords. Only the investigators have permissible access to the study records. Consents will be kept in a locked drawer in a secure room that requires keypad access. No names will attach to the surveys, audits or tapes; they will be labeled only with the unique code. At the end of the study, we will delete the zoom recordings. Indicate if data will be collected, downloaded, accessed, shared or stored using a server, desktop, laptop, external drive or mobile device (including a tablet computer such as an iPad or a smartphone (iPhone or Android devices) that you have not already identified in the preceding questions □ I will use a server not previously listed to collect/download research data ☑I will use a desktop or laptop not previously listed HHS location for HHS patients □ I will use an external hard drive or USB drive ("flash" or "thumb" drives) not previously listed

- ☐ I will use a mobile device such as an tablet or smartphone not previously listed
- 18.8 Consultants. Vendors. Third Parties. Not applicable
- 18.9 Links to identifiable data:
- 18.10 Sharing of Data with Research Team Members: Data will be shared within the University of Minnesota's Box.
- 18.11 Storage and Disposal of Paper Documents: Any paper documents generated at the HHS sites will be stored on-site in the research offices HHS. The office space is secured by key-card or door-code access only. All study documents will be stored through the required length of storage outlined by the study protocol and grant materials. Likewise, M-Health documents will be stored on M-Health site.

